### **8.2. PROTOCOL ADHERENCE**

The Investigator must read the protocol thoroughly and must follow the instructions exactly. Any change should be agreed upon by prior discussion between the Sponsor and the Investigator, with appropriate written protocol amendments made prior to implementation of the agreed-upon changes.

### **8.2.1. Changes in Study Conduct/Statistical Analyses/Amendments**

No change in the conduct of the study should be instituted without written approval from the Sponsor. Any amendment containing major modifications (particularly if it may involve an increased risk to the subjects) will require written approval from the Sponsor and IRB/IEC before it may be implemented.

### **8.3. INSTITUTIONAL REVIEW BOARD /INDEPENDENT ETHICS COMMITTEE**

This study, all appropriate amendments, all advertising, and written materials given to the subjects will be reviewed and approved by an IRB/IEC, prior to use.

### **8.4. SUBJECT INFORMATION AND CONSENT**

The study personnel will inform all subjects in this study in accordance with GCPs, about the study. The study personnel will review the informed consent form (ICF) with each subject and give the subject an opportunity to read the consent and have all questions answered before proceeding. A current written consent form, approved by an IRB, is to be supplied by the Investigator and willingly signed by each subject, or their legal guardian, prior to initiating any study procedures, including instructing the subject to discontinue the use of medications requiring wash-out. A written assent form, approved by

an IRB, is to be supplied by the Investigator and willingly signed by each subject who is legally not able to sign an informed consent form, as required, in accordance with IRB guidelines for providing assent. The Investigator is responsible for maintaining each subject's consent form and assent form, if applicable, in the study file and providing each subject with a copy of the signed form(s).

## **8.5. RECORD KEEPING**

### **8.5.1. Data Collection**

The Investigator must maintain detailed records on all study subjects. Data for this study will be appropriately documented in the source documents and entered into eCRFs through the eDC system provided by the Sponsor's designated data management group. Applicable data from the subject's source documents should be recorded in the eCRFs completely, promptly, taking time to correct any mistakes as prompted by the eCRF system.

Throughout the study, representative(s) of the Sponsor (e.g., CRO's Monitor) will review the appropriate eCRF pages. eCRFs should be completed and ready for review by the Sponsor/CRO's Monitor, within one (1) week of each study visit for a given subject.

### **8.5.2. Data Corrections**

Corrections of data entered into the eCRF must be made in the system for electronic case report forms and supported by source documents, as appropriate.

- The Sponsor's Monitor will review the eCRFs, evaluate them for completeness and accuracy, and ensure that all appropriate information is entered.
- No changes will be made to the data on the eCRF pages after the data are determined to be final by the Sponsor's Monitor and data management group. Corrections to the eCRF through queries and comments will be tracked by the eCRF internal audit trail as outlined in the eDC system.

### **8.5.3. Source Documentation**

Investigators must keep accurate separate records (other than the eCRF) of all subjects' visits, which include all pertinent study-related information including the original signed/dated informed consent and assent forms, and drug accountability records. As a minimum, a statement should be made in the subject's record indicating that the subject (or caregiver) has signed an informed consent form and has been enrolled in Protocol CLS006-CO-PR-002.

Any AEs must be thoroughly documented. Results of any diagnostic tests conducted during the study should also be included in the source documentation. Relevant telephone conversations with the subject and/or the Sponsor/CRO concerning the study must also be recorded.

#### **8.5.4. Monitoring/Auditing**

Representatives of the Sponsor, following GCP guidelines, will monitor the conduct of the study. In addition, inspections or on-site audits may be carried out by the FDA, local regulatory authority or by the Sponsor's independent Quality Assurance Department. The Investigator will allow the Sponsor's representatives and any regulatory agency to examine all study records, eCRFs, corresponding subject medical records, clinical drug dispensing records, drug storage area, and any other documents considered source documentation.

#### **8.5.5. Archives**

Records must be retained in accordance with the current ICH Guidelines on GCP. All essential study documents including records of subjects, source documents, eCRFs and study drug inventory must be kept on file.

Essential documents should be retained until at least 2 years after the last approval of a marketing application in an ICH region and until there are no pending or contemplated marketing applications in an ICH region, or until at least 2 years have elapsed since the formal discontinuation of clinical development of the investigational products. However, essential documents may be retained for a longer period if required by the applicable regulatory requirements or by agreement with the Sponsor. The Sponsor is responsible for informing the Investigator when these documents no longer need to be retained. The Investigator will not dispose of any records relevant to this study without written permission from the Sponsor, and will provide the Sponsor the opportunity to collect such records.

The Investigator shall take responsibility for maintaining adequate and accurate source documents of all observations and data generated during the study. Such documentation is subject to inspection by the Sponsor, its representatives, and regulatory authorities. If the Principal Investigator retires, relocates, or for other reasons withdraws from the responsibility of keeping the study records, custody must be transferred to a person who will accept the responsibility and the Sponsor must be notified in writing of the name and address of the new custodian.

### **8.6. CONTRACTUAL REQUIREMENTS**

A contractual agreement will be signed between the Sponsor/CRO and the Investigator. This document will contain complementary information, i.e. financial agreement, confidentiality, study payment schedule, and publication of study results.

### **8.7. PUBLICATION POLICY**

All data generated from this study are the property of the Cutanea Life Sciences, Inc. Publication of data will be done in accordance with the contractual agreement between the Sponsor/CRO and Investigator/clinical site.

## APPENDIX A: STUDY DRUG APPLICATION INSTRUCTIONS

For this research, it's important to standardize the way study drug is applied to each wart. Please read these instructions carefully.

[figure not shown]
### APPLY STUDY DRUG ONCE DAILY, AS DIRECTED.

- Study drug must be used to treat the wart(s) **ONLY** as directed by study personnel.
- For children under the age of 12, an adult caregiver (a parent/guardian) should apply the study drug.
- Each wart needs to be treated daily (one time per day) or until advised to stop by study personnel.
  - \* Choose a regular time each day, based on convenience, to apply the study drug (e.g., in the morning after showering or in the evening prior to bedtime). If you/your child are not able to apply the study drug at the regular time, you/your child should still apply but be careful, you/your child should not apply the gel on the wart more than 1x per day.

#### Applying study drug:

1. Wash, rinse and thoroughly dry your (or your child's) hands before applying study drug.
2. Remove the cap from the study drug tube and squeeze a **small amount** of the study drug gel (see photo) to cover each wart as directed by study personnel.
3. Gently rub the gel into the wart for approximately **20 seconds** or until the gel is fully absorbed.

**!** \* Avoid contact with your (or your child's) eyes, mouth, and inside the nose. If study drug comes in contact with eyes, flush the area with water.  
\* Avoid contact with others while the gel dries.

#### After applying study drug:

1. Return the cap to the study drug tube and store the study drug tube at room temperature.
2. Record each study drug application in the study diary provided.
3. Keep the skin dry as long as possible, **at least for an hour!**
  - \* **Unless hands are being treated**, wash hands after application.
  - \* DO NOT apply bandages or dressings to the treated wart(s).
4. If the study drug is applied by an adult caregiver (a parent/guardian), they will need to wash their hands after application.

\* **Reminder:** Bring the study drug tube and study diary to the clinic at EVERY visit; **do NOT discard the study drug tube (even if it's empty)!** Please call the clinic immediately if you have lost the tube.

## 2.0 Purpose

The statistical analysis plan (SAP) describes the statistical methods to be used during the reporting and analyses of data collected under Cutanea Life Sciences, Inc. Protocol CLS006-CO-PR-002.

## 3.0 Scope

This plan is a living document that will be created during the trial start-up. The Statistical Analysis Plan will be finalized prior to database lock. SAP will require sign off from the Project Manager and the sponsor.

The Statistical Analysis Plan outlines the following:

- Study objectives
- Study design
- Variables analyzed and analysis sets
- Applicable study definitions
- Statistical methods regarding important protocol deviations, study drug exposure, efficacy analysis, concomitant medications, adverse events handling, laboratory data and physical examinations

## 4.0 Introduction

This statistical analysis plan (SAP) describes the statistical methods to be used during the reporting and analyses of data collected under Cutaneous Life Sciences, Inc. Protocol CLS006-CO-PR-002.

This SAP should be read in conjunction with the study protocol and case report form (CRF). This version of the plan has been developed using the protocol dated 23May2017 and CRF dated 02Aug2017. Any further changes to the protocol or CRF may necessitate updates to the SAP.

### 4.1 Changes from Protocol

No changes as of this version of the SAP.

## 5.0 Study Objectives

The objective of this study is to evaluate the efficacy and safety of six (6) weeks of once daily application of Furosemide Topical Gel 0.125% (CLS006) compared to vehicle in subjects  $\geq 2$  years of age with nongenital cutaneous common warts (verruca vulgaris).

---

## 6.0 Study Design

The study will be conducted as a randomized, double-blind, vehicle-controlled, parallel group, multicenter study at approximately 40 sites involving approximately 480 subjects (~240 per treatment group) with nongenital cutaneous common warts. Approximately 160 subjects enrolled will be pediatric subjects (~80 will be  $\geq 2$  to  $<12$  years of age and ~80 will be  $\geq 12$  to  $<18$  years of age). Subjects may be in the study up to 34 weeks.

**Table 1 Schedule of Visits and Study Assessments**

Study Period	Screening	Double-Blind Treatment (DBT)					Post-treatment Efficacy Evaluation (PTEE)		Follow-up 	
Visit	Screening	Baseline	Week 2	Week 4	Week 6 / End of Treatment (or Early Term during DBT Period)	Week 12	Week 18 / End of Post-tx Efficacy Evaluation (or Early Term during PTEE Period)	Follow-up #1	Follow-up #2 (Final)	
Time	Day -28 to -1	Day 1	Day 14	Day 28	Day 42	Day 84	Day 126 (3 mon post-treatment)	Week 24	Week 30 (6 mo. post-treatment)	
Procedures (Visit Window)	( $\pm$ 3 days)					( $\pm$ 5 days)		( $\pm$ 7 days)		
Informed Consent	X									
Demographics & Medical/Medical/Surgical History	X	X 								
Prior & Concomitant Medication/Treatment	X									
Limited Physical Exam 	X				X					
Vital Signs (BP, HR)	X	X	X	X	X	X	X			
ECG	X									
Urine Pregnancy Test 	X	X			X					
Clinical Safety Lab Testing (Hematology, Chemistry)	X				X					
Wart Assessments	X	X	X 	X 	X 	X 	X 	X 	X 	
Clinical Photography (select sites only)		X			X		X			
Inclusion/Exclusion Criteria	X	X								
Enroll/Randomization		X								
Dispense Study Drug & Diary		X	X	X						
Treatment Compliance / Collect and Review Study Drug & Diary			X	X	X					
Apply Study Drug (Once Daily)		X 								
Concomitant Medication/Treatment Review		X	X	X	X	X	X	X 	X 	
Adverse Events		X 	X	X	X	X	X			

1 Only required for subjects who achieved clearance of at least one treated wart as determined by the PI or an appropriately qualified Sub-I at week 18 / End of Post-tx Efficacy Evaluation.

2 Adverse event assessment will be performed following the first study drug application (any changes in subject's health before first study drug application should be recorded as medical history).

3 A limited physical exam (refer to Section 7.5.2 of the protocol) including height & weight measurements at Screening and weight

---

measurement only at the Week 6/EOT (or Early Termination during DBT Visit).

- 4 Urine pregnancy test for women of childbearing potential only. Urine pregnancy testing should also be conducted at any visit for any female who is suspected of being pregnant.
- 5 New common warts that appear after the Baseline visit will be identified, characterized and location recorded/mapped only, but not treated.
- 6 Clinical Photography will be optional for subjects < 12 years of age.
- 7 The first application of study drug will be performed under supervision at the study center.
- 8 Concomitant medication/treatment review at Follow-up visit will focus on review of restricted concomitant medication/treatment only (refer to Section 7.6.10.1 of the protocol).

## 6.1 Sample Size Considerations

The sample size estimates for the current study are based upon the rates of clearance of warts in the previous Phase 2 study [REDACTED]. This was a randomized, double blind, vehicle controlled, Phase II study in 80 subjects who were treated with topical [REDACTED], furosemide, [REDACTED], or vehicle for 42 days daily with an 8-week follow-up period. For the furosemide treatment group, the proportion of subjects with all cleared warts was 0.1 (10%) versus 0 in the vehicle.

The difference in the proportion of subjects with all treated warts cleared (complete clearance) at the Week 18/End of Post-Treatment Efficacy Evaluation period (EOS) is the primary endpoint of the current study. For conservative purposes, assuming 10% and 2% complete clearance rates in the furosemide and vehicle treated groups, respectively, 200 subjects randomized per treatment group will provide for 92% power at a two-sided  $\alpha$  of 0.05 to detect a difference between active and vehicle treated groups.

With the inclusion of an additional 80 subjects in the  $\geq 2$  to  $< 12$  cohort, the total sample size of 480 will provide 96% power with the assumption unchanged.

## 6.2 Randomization

Subjects that meet all inclusion and exclusion criteria will be randomized to one of two treatment groups in a 1:1 ratio for each study center according to a predetermined computer-generated randomization code.

Subjects will be randomized to treatment using an Interactive Web Response System (IWRS). The randomization scheme will include age stratum at 3 levels ( $\geq 2$  to  $< 12$ ,  $\geq 12$  to  $< 18$  or  $\geq 18$ ) and investigative site.

# 7.0 Study Variables and Covariates

## 7.1 Primary Efficacy Variable

Proportion of subjects with complete clearance of all treated warts (i.e., Baseline Treated warts) between the active and vehicle at Week 18 /End of Post-treatment Efficacy Evaluation.

## 7.2 Secondary Efficacy Variables

- The ratio of cleared warts to all treated warts for each subject at Week 18/End of Post-treatment Efficacy Evaluation.
- Proportion of subjects with complete clearance of all treated warts at Week 12, then Week 6/EOT.
- The ratio of cleared warts for each subject to all treated warts at Week 12, then Week 6/EOT.
- Reduction from baseline in wart size of treated warts at Week 18/End of Post-treatment Efficacy Evaluation

## 7.3 Tertiary Efficacy Variables

- All endpoints at all other time-points.
- Evaluation of durability of response and incidence of recurrence of treated warts from Week 18 end of post-treatment efficacy evaluation period to Week 30 the end of the follow-up period.

## 7.4 Other Variables

- New common warts that appear after Baseline by visit

## 7.5 Safety Variables

Safety variables including AEs, vital signs, and laboratory parameters will be collected according to the Schedule of Visits and Study Assessments (refer to Table 1).

## 7.6 Predetermined Covariates and Prognostic Factors

Subject age ( $\geq 2$  -  $< 12$ ,  $\geq 12$  -  $< 18$ , and  $\geq 18$ ) and investigator site will be used as covariates for Cochran-Mantel-Haenszel (CMH) analyses.

Baseline Treatment Wart size (i.e., diameter) will also be included as a covariate in the analysis of covariance (ANCOVA).

# 8.0 Definitions

## Baseline and Change from Baseline

Baseline is defined as the last available pre-dose value.

Change from Baseline = (post-Baseline value – Baseline value). For the purpose of tabulations, the unscheduled post-Baseline values generally will be excluded.

## Completion of study

The completion of study is defined as an answer of “Yes” to the question “Did the subject complete the study at Week 18?” on the form of Study Completion in the CRF.

## Prior and Concomitant Medications

Prior medications will be any medication with a start date before the first day of treatment.

Concomitant medications are defined as any medications ongoing at the start of treatment or with a start date on or after the first dose date. Consequently, medications ongoing at the start of treatment will be reported as both prior and concomitant medications.

## Treatment-Emergent Adverse Events

Treatment emergent AEs (TEAEs) are defined as AEs whose onset occurs, severity worsens or intensity increases after receiving the study medication. Events which occur more than thirty days after the last dose of study medication will not be considered treatment emergent. Adverse Events will be considered treatment-emergent if they have missing or have partial start dates for which it cannot be determined whether the AE started before or after the first dose of study medication.

## Adverse Events with Outcome of Death

Any AE with an outcome of fatal will be considered as AE with an outcome of death.

## Imputation of AE (for determination of TEAE only) and concomitant medication start and stop dates:

**Start Date:** If only ‘day’ is missing, and the month and year are not the same as the month of first dose, then impute day with ‘01’. Otherwise, if the month and year are the same as the first dose date, use the first dose date. If ‘day’ and ‘month’ are missing, and ‘year’ is not missing, then impute month and day with month and day of the first dose date (assuming same ‘year’). If ‘day’ and ‘month’ are missing and ‘year’ is not missing and is not the same year as first dose date, then impute with ‘01’ for both ‘day’ and ‘month’. If the start date is completely missing, it will be set to the first dose date.

**Stop Date:** If only ‘day’ is missing, impute day with last day of the month. If ‘day’ and ‘month’ are missing, and ‘year’ is not missing, then impute month with ‘12’ and day with ‘31’ (or date of study discontinuation/completion if earlier than 12-31 and year is the same as the year of discontinuation). If the stop date is completely missing, it will be set to the date of study discontinuation/completion. A stop date will not be applied to ongoing AEs.

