#### **7.3.2.1. Screening**

Screening Visit procedures are to be conducted within 28 days prior to the subject's Baseline (Day 1) Visit.

The following procedures will be performed during Screening:

1. Obtain subject's and/or his/her legal guardian(s) for subjects under the legal age of consent, written informed consent prior to initiating any study procedures, including instructing the subject to discontinue excluded medications/treatments.
  - a. Subjects who are under the legal age of consent are to provide written informed assent as required, according to IRB guidelines for obtaining assent;
  - b. Provide subject and/or his/her legal guardian(s) with a copy of the signed and dated consent form (and assent form, if applicable);
  - c. Document informed consent in the subject's medical record.
2. Obtain demographics including subject reported race and ethnicity.
3. Screen the potential subject according to the study inclusion/exclusion criteria (refer to Sections 7.2.1 & 7.2.2).
4. Perform an in-office urine pregnancy test on all females of childbearing potential.
5. Review and record medical/surgical history including:
  - a. Wart history;
  - b. Identification of any history of significant cardiovascular, hepatic or renal disease.
6. Review and record prior and concomitant medications/treatments (refer to Section 7.6.10) including:
  - a. Wart medications/treatments used within one year;
  - b. All non-wart medications/ treatments used within 1 month;
  - c. Washout medications/treatments, if applicable.
7. Obtain vital signs.
8. Perform wart assessments (refer to Section 7.4.1).
9. Perform a limited Physical Exam including height and weight measurements (refer to Section 7.5.2).
10. Perform a 12-lead electrocardiograph (ECG) (refer to Section 7.5.5).
11. Collect blood samples for clinical safety laboratory testing (hematology, chemistry).
12. As appropriate, schedule the Baseline (Day 1) visit, to occur after the results of the clinical safety laboratory tests are received and any required washout period has been completed.

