### **9.3 Per Protocol**

The Per-Protocol (PP) analysis set will include all subjects in the ITT population who complete 6 weeks of treatment and 12 weeks of post-treatment efficacy evaluation without any major deviations from the protocol. The subjects to be included in the PP analysis population will be determined by the Sponsor prior to the unblinding of the study. The PP population will be used as secondary for the primary endpoint only.

Subjects potentially excluded from the PP population will be based on the following criteria and reviewed by the clinical team:

- 1 - Subjects who have not completed 6 weeks of treatment and 12 weeks of post-treatment efficacy evaluations
- 2- Subjects less than 2 years of age
- 3 - Subjects with more than 6 common warts at baseline
- 4 - Subjects without a pre-treatment wart assessment
- 5 - Subject who have taken an excluded prior and concomitant medications / therapies as listed in the protocol
- 6 - Subjects whose warts are not present for at least 4 weeks before treatment (baseline) as reported in Medical History
- 7 - Subjects with clinically significant dermatological disorders in the treatment area
- 8 - Subjects who require ongoing treatment with furosemide
- 9 - Subjects whose study drug compliance is as follows: missing more than 12 doses in total throughout the study
- 10 - Subjects with week 18 visits out of window more than 14 days outside the target visit date

---

- 11 - Subjects who received the wrong assigned treatment medication
- 12 – Subjects who violated key inclusion/exclusion criteria

Subject listings will be provided to the Sponsor based on the above criteria for review and final determination of the PP population. Subjects to be excluded from the PP will be determined before the study is unblinded and listed in a separate document.

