## 12.2 Important Protocol Deviations

Important protocol deviations (IPD) are a subset of protocol deviations that might significantly affect the completeness, accuracy, and/or reliability of the study data or that might significantly affect a subject's rights, safety, or well-being.

Protocol deviations will be determined based on programmed checks of the study database. These Protocol deviations are based on the following categories deemed to be important:

1. Subjects that violate key inclusion/exclusion criteria
2. Subjects who received the wrong treatment
3. Subjects who received prohibited medications/treatment during the trial
4. Subjects who met withdrawal criteria but were not withdrawn
5. Subjects who did not have necessary data collected to interpret the primary endpoint
  - a. Missed Week 18 visit
  - b. Week 18 more than 14 days outside target visit date
6. Subjects with a deviation that significantly affects safety or well-being
  - a. Physical exam, labs or ECG not performed at screening prior to randomization
  - b. Week 6 physical exam or labs not performed
  - c. Pregnancy test not preformed prior to randomization
  - d. Pregnancy test not performed at Week 6

---

For reporting proposed Protocol Deviations will be assigned to the following categories: Inclusion Criteria, Exclusion Criteria, Study Drug, Assessment Safety, Visit Window, and Prohibited concomitant medications.

The protocol deviation list will be finalized prior to the database lock, and important protocol deviation data will be listed and tabulated using incidence by deviation type.

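### The SAP's date rule for medications can give a treatment stopped before first dose a start date after its stop, and so class it as concomitant and not prior

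*SAP*

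**What the plan says.** SAP 8.0 (Definitions) has one set of date rules for adverse events and concomitant medications. For a start date with nothing recorded: "If the start date is completely missing, it will be set to the first dose date". For a start with only the year known, in the year of first dose: "then impute month and day with month and day of the first dose date". A year-only start in another year becomes 1 January of that year. Stop dates are imputed separately. For example: "If the stop date is completely missing, it will be set to the date of study discontinuation/completion". No rule compares the start with the stop.

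The same section then classifies medications. "Prior medications will be any medication with a start date before the first day of treatment". A medication is concomitant if it is ongoing when treatment starts, or if its start date is on or after the first dose date. That second condition does not mention the stop date.

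Protocol 7.6.10 defines concomitant by use at or after the Baseline visit, and SAP 4.1 reports no changes from the protocol.

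Protocol 7.3.2.1 has sites record at Screening "Wart medications/treatments used within one year", and also any washout treatments. Protocol 7.6.10.1 prohibits other wart treatment during the study.

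**The concern.** Setting an unknown start to the first dose date is the cautious choice for adverse events, because it makes a doubtful event treatment-emergent. For medications the same rule can override a recorded fact. If the stop date shows that the treatment ended before first dose, a start on the first dose date is impossible. The classification nevertheless rests on that start date.

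The records most exposed are the ones this trial sets out to collect. A start date recalled over as much as a year may well be incomplete. The stop date matters for the washouts of 4, 8 or 12 weeks in Protocol 7.2.2, so it is more likely to be known. A wart therapy that was stopped correctly could then look like wart therapy used on study.

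Two later steps could pick this up. For deviations, SAP 12.2 says "Protocol deviations will be determined based on programmed checks of the study database", and prohibited treatment during the trial is one of its categories. Among the grounds for possible per-protocol exclusion, SAP 9.3 lists "Subject who have taken an excluded prior and concomitant medications / therapies as listed in the protocol".

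**Working it through.** The plan gives no figure here, so the check applies the SAP 8.0 rules literally to test records.

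**Inputs.** The start, stop, prior and concomitant rules are those of SAP 8.0. The dates are assumed: first dose on 16 Oct 2017, Week 18 completion on 18 Feb 2018 (Day 126), and a wart treatment stopped on 11 Sep 2017. The gap from 11 Sep to 16 Oct is 19 + 16 = 35 days, which satisfies a four-week washout.

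**Formulas.**
- Duration = stop − start + 1.
- Prior = start before first dose.
- Concomitant = start on or after first dose, or ongoing at first dose.
- Proposed guard: start = the earlier of the imputed start and the stop.

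| Record | Start under SAP rule | Stop | Duration (days) | Class under SAP | Class with guard |
|---|---|---|---|---|---|
| Start missing, stop 11 Sep 2017 | 16 Oct 2017 | 11 Sep 2017 | −35 + 1 = −34 | concomitant, not prior | start 11 Sep 2017; prior only |
| Start 2017 only, stop 11 Sep 2017 | 16 Oct 2017 | 11 Sep 2017 | −34 | concomitant, not prior | start 11 Sep 2017; prior only |
| Start 2016 only, stop 11 Sep 2017 | 1 Jan 2016 | 11 Sep 2017 | 619 + 1 = 620 | prior only | unchanged |
| Start missing, stop 2017 only | 16 Oct 2017 | 31 Dec 2017 (imputed) | 76 + 1 = 77 | concomitant, not prior | unchanged |

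The first two rows show the defect. Use ended 35 days before first dose, so the record is not concomitant under Protocol 7.6.10, yet SAP 8.0 makes it so. The third row shows that a year-only start in an earlier year is handled correctly. The fourth shows that the guard stays cautious: without evidence that the stop came before first dose, the record remains concomitant.

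**Size.** The documents give no rate of incomplete start dates. For scale only, if 1% of the 480 planned subjects had such a record, 0.01 × 480 = 4.8, or about 5 subjects, would be affected. At 5% it would be 0.05 × 480 = 24. Both rates are assumptions.

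**The case against.** The strongest reply is about scope. The SAP heading speaks of concomitant medication, and a drug known to have stopped before first dose is not concomitant in the ordinary sense or under the protocol. A sensible programmer might never apply the rule to it. That may well happen, but the SAP does not say so. Its test for concomitant uses the very start date being imputed, and nothing requires the start to be on or before the stop.

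Other objections succeed and limit the point:

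- **Ongoing medication.** A reader might infer that ongoing drugs with an unknown start are lost from the prior table. SAP 8.0 states that medications ongoing at the start of treatment are reported as both prior and concomitant, so that case is already covered.
- **Day missing in the first-dose month.** Here too the SAP says "if the month and year are the same as the first dose date, use the first dose date". A reader might extend the concern to washed-out wart therapy by this route. With at least 28 days between stop and first dose in one calendar month of at most 31 days, the therapy would have to start and stop by day 3 (31 − 28). That hardly ever fits.
- **False deviations.** A reader might infer that the programmed checks will flag these records. SAP 12.2 does not say whether the checks use imputed or recorded dates, so a false flag is possible, not certain.
- **Double-blind tabulation.** SAP 12.3.2 plans a display for the double-blind period without defining how use in that period is derived. A recorded stop before Day 1 could keep the record out of it.
- **No correction.** SAP 11.2 provides for data-issue logs and for output review before lock, which may catch a start after a stop, although this check is not named. Under SAP 9.3 the clinical team reviews possible per-protocol exclusions and the Sponsor decides before unblinding. That criterion already covers excluded prior therapies, so prior wart treatments come under review in any case.

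**Conclusion.** The point holds as a minor drafting defect. Applied literally, SAP 8.0 misclassifies a medication whose stop before first dose is recorded and whose start is completely missing or year-only in the first-dose year. The result contradicts Protocol 7.6.10.

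The effect is confined to the medication tables and a possible false entry on the deviation list or in the per-protocol review. It rests on two assumptions: that such records occur, which the one-year look-back makes plausible but the documents do not quantify, and that the rule is programmed as written.

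A reader might be tempted to compare the number of affected records with the number of clearances expected and see a threat to the efficacy result. The documents do not support that. Misclassified medication records do not change any clearance count, and the primary analysis includes all randomized subjects regardless of medication use.

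**What to change.** Add two sentences to SAP 8.0, for medications only:

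1. An imputed start date may not be later than the recorded or imputed stop date.
2. A medication whose stop date precedes the first dose date is prior only.

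Leave the adverse event rule as it is. No new clause is needed for ongoing medications. The cost is two sentences and about one line of derivation code before database lock. No data collection changes, and records without evidence of a stop before first dose remain concomitant. While the section is open, it would help to state in SAP 12.2 whether the prohibited-medication check uses recorded or imputed dates.
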